8.4.6. Analysis of Covariates

The following covariate analyses will be conducted for the primary and secondary efficacy based on the ITT population to evaluate the treatment effect adjusted for the three covariates listed in Section 4.6:

- The primary analysis model (Section 8.4.2) adding an individual covariate of the three covariates will be used to obtain the 2-sided 95% confidence intervals for the covariate-adjusted estimate of the treatment effect and covariate effect along with their respective p-values.
- The primary analysis model (Section 8.4.2), adding all three covariates will be used to obtain the 2-sided 95% confidence intervals for the covariate-adjusted estimate of the treatment effect.

8.4.7. Exploratory Efficacy Endpoints

Each exploratory efficacy endpoint (described in Section 4.3, except for PGIC and Semmes-Weinstein monofilament testing) will be analyzed in a manner similar to the corresponding continuous or categorical Repeated Measures Models for the primary analyses described in Section 8.4.2 based on available data of ITT population.

For each such parameter, a repeated measures model analysis will be used accounting for all post-baseline visits where the parameter is collected. The model will include treatment, visit, baseline use of gabapentin and/or pregabalin, and treatment-by-visit interaction as fixed effects and baseline measurement of the parameter as a covariate. An unstructured variance-covariance matrix for the repeated measures model will be used unless convergence problems arise. The point estimate for the least-squares mean of the treatment difference (VM202 – Placebo) and the corresponding two-sided 95% confidence interval at each visit will be summarized.

The 7-category data for PGIC will be combined into 3-category data (1: very much improved, much improved, 0: minimally improved, no change, minimally worse, -1: much worse, very much worse). PGIC will be analyzed at each follow-up visit by Cochran-Mantel-Haenszel (CMH) test to account for the stratification variable and row means scores differ statistic (row variable: treatment group, column variable: 3-category data of PGIC) will be used.

A graph of the cumulative proportion of responders will be generated at each of the 3-, 6-, and 9-month follow-up visits to predict the likelihood of a response for each treatment group and level of the stratification variable (i.e., baseline use of gabapentin and/or pregabalin) over the indicated range of response cutoff-points (20% to 70%) for the reduction from baseline in the average 24-hour pain score.

Semmes-Weinstein monofilament testing will be conducted at 5 testing sites on each foot; each testing site will be graded based on Table 5. Shift tables of grade at baseline versus grade at follow-up (i.e., a 7-by-7 contingency table) will be provided to summarize changes for each testing site by treatment and stratification factor at each follow-up visit. A proportional-odds cumulative logit model with categorical terms for treatment, stratification factor, and baseline grade will be applied for each testing site at each follow-up visit based on the observed data in the ITT population. Multivariate cumulative logits to account for the within subject correlation between testing sites may be considered.

Force (gms)	Interpretation	Grade Points
0.07	Normal	6
0.4	Diminished Light Touch	5
2.0	Diminished Protective Sensation	4
4.0	Mild Loss of Protective Sensation	3
10	Moderate Loss of Protective Sensation	2
300	Deep Pressure Sensation Only	1
>300	No Sensation	0

TABLE 5. Grading Scale for Semmes-Weinstein Monofilament Testing

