4.2.10. SEMMES WEINSTEIN MONOFILAMENT TEST

The Semmes-Weinstein monofilament test will be conducted at Day 0, 90 Days, Day 180 (6 months) and Day 270 (9 months). Testing will be performed on the plantar aspect of great toe, first, third and fifth metatarsal heads of each foot. The Semmes Weinstein monofilament test instructions can be found in Appendix 6.

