Appendix 6. Semmes Weinstein Monofilament Testing

Directions for use of Semmes – Weinstein Monofilament Testing³

- 1. Assess integrity of monofilament (no bends/breaks).
- 2. Show the monofilament to the client. Place the end of the monofilament on his/her hand or arm to show that the testing procedure will not hurt.
- 3. Ask the client to turn his/her head and close his/her eyes or look at the ceiling.
- 4. Hold the monofilament perpendicular to the skin.

- 5. Place the end of the monofilament on the sole of the foot. Ask the subject to say 'yes' when he/she feels you touching his/her foot with the monofilament. DO NOT ASK THE SUBJECT, "did you feel that?" If the subject does not say 'yes' when you touch a given testing site, continue on to another site. When you have completed the sequence RETEST the area(s) where the subject did not feel monofilament.
- 6. Push the monofilament until it bends, then hold for 1-3 seconds.
- 7. Lift the monofilament from the skin. Do not brush or slide along the skin.
- 8. Repeat the sequence randomly at each testing site on the foot (see pictures below).

ALL TESTING IS PERFORMED BILATERALLY (ON BOTH FEET)

Sites on the sole of the foot for monofilament testing

PLANTAR ASPECT OF GREAT TOE, FIRST, THIRD AND FIFTH METATARSAL HEADS OF EACH FOOT

Dorsal aspect of the great toe for monofilament testing

The same location used for the MNSI assessment will be tested, specifically, filaments are applied to the dorsum of the great toe midway between the nail fold and the DIP joint.

Testing with the monofilaments begins with filaments in the normal threshold level and progresses to filaments of increasing pressure until touch is identified by the subject. The smallest monofilament (lowest grams) that can be felt by the subject should be indicated for each

³ Use of Semmes-Weinstein Monofilament Testing – Nursing Best Practices Guidelines http://pda.rnao.ca/content/use-semmes-weinstein-monofilament (downloaded 14Oct14)

location. Filaments should be applied a minimum of three times, with one response out of three taken as an affirmative response.

The following filaments will be used.

Filament	Force (g)	Interpretation			
2.83	0.07	Normal			
3.61	0.4	Diminished Light Touch			
4.31	2.0	Diminished Protective Sensation			
4.60	4.0	Mild Loss of Protective Sensation			
5.07	10	Moderate Loss of Protective Sensation			
6.65	300	Deep Pressure Sensation Only			

Notes

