4.3. Exploratory Efficacy Endpoints

- The change in the average 24-hour pain score from baseline to the 9-month follow-up [Day 270] (6 months after the Day 90 injection) obtained from the Daily Pain and Sleep Interference Diary.
- The outcome of at least a 50% reduction (i.e., ≥ 50%) in the average 24-hour pain score from baseline to the 9-month follow-up [Day 270] (6 months after the Day 90 injection) obtained from the Daily Pain and Sleep Interference Diary.
- The outcome of at least a 20%, 30%, 40%, 60%, or 70% reduction in the average 24-hour pain score from baseline to the 3-month follow-up obtained from the Daily Pain and Sleep Interference Diary
- The outcome of at least a 20%, 30%, 40%, 60%, or 70% reduction in the average 24-hour pain score from baseline to the 6-month follow-up obtained from the Daily Pain and Sleep Interference Diary

- The outcome of at least a 20%, 30%, 40%, 60%, or 70% reduction in the average 24-hour pain score from baseline to the 9-month follow-up obtained from the Daily Pain and Sleep Interference Diary
- Change in VAS for Pain from baseline to the 3-month, 6-month, and 9-month follow-up; note that VAS is read by 2 different investigators at each assessment and the average of the two scores will be used for analysis
- Michigan Neuropathy Screening Instrument (MNSI) physical assessment and history changes from baseline to the 6-month and 9-month follow-up
- Change in average sleep interference score from baseline to the 3-month, 6-month, and 9-month follow-up obtained from the Daily Pain and Sleep Interference Diary
- BPI-DPN pain interference score changes from baseline to the 3-month, 6-month, and 9-month follow-up; note that an average score of BPI-DPI pain interference will be analyzed
- BPI-DPN pain severity score changes from baseline to the 3-month, 6-month, and 9-month follow-up; note that not only an overall average score of BPI-DPN pain severity but also each individual severity components (worst pain, least pain, average pain, pain now) will be analyzed
- Patient's Global Impression of Change (PGIC) at the 3-month, 6-month, and 9-month follow-up
- Semmes-Weinstein monofilament testing changes from baseline to the 3-month, 6-month, and 9-month follow-up.

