7.4. Multiplicity Adjustment

There is no adjustment of the type 1 error rate based on multiplicity. A step-down approach will be used that controls for the potential inflation of the type 1 error rate.

The analyses of the primary efficacy endpoints will be conducted hierarchically based on the order of the two primary efficacy endpoints. Similarly, the analyses of the two secondary efficacy endpoints will be conducted hierarchically based on the corresponding order for the two secondary efficacy endpoints. The secondary efficacy endpoints will be tested only when the null hypotheses of both the primary efficacy endpoints are rejected at a significance level of 0.05^2 .

The significance level for each exploratory efficacy endpoint will be 0.05.

All statistical testing will be 2-sided.

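### The exploratory monofilament endpoint is split into 30 separate models, and the SAP commits to no overall comparison

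*SAP*

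**What the plan says.** SAP 4.3 lists a single exploratory endpoint: "Semmes-Weinstein monofilament testing changes from baseline to the 3-month, 6-month, and 9-month follow-up". SAP 8.4.7 then states that "Semmes-Weinstein monofilament testing will be conducted at 5 testing sites on each foot", grades each site from 0 to 6 (Table 5), and specifies a proportional-odds cumulative logit model with terms for treatment, stratification factor and baseline grade. That model "will be applied for each testing site at each follow-up visit based on the observed data in the ITT population".

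On combining sites, the SAP says only: "Multivariate cumulative logits to account for the within subject correlation between testing sites may be considered". It gives no trigger, estimand or role for that model. Visits are not combined either, because the repeated measures model of SAP 8.4.7 covers the exploratory endpoints "except for PGIC and Semmes-Weinstein monofilament testing".

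On the significance level, SAP 7.4 says: "The significance level for each exploratory efficacy endpoint will be 0.05". It does not say how the level is shared when one endpoint produces many tests.

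The count of five sites per foot is sound. Protocol 4.2.10 names four, the "plantar aspect of great toe, first, third and fifth metatarsal heads of each foot", and Protocol Appendix 6 adds a fifth, where "filaments are applied to the dorsum of the great toe midway between the nail fold and the DIP joint".

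**The concern.** One endpoint yields 30 treatment comparisons, and nothing marks any of them, or any combination, as the answer. No total score, foot-level score, main site, main visit or common treatment effect is named.

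Two things follow. A few nominally significant cells out of 30 could be presented as sensory improvement although they are compatible with chance. In the other direction, a modest effect spread over the whole foot could be lost in a mixed set of site results, because each site is tested alone. Leaving the joint model optional adds a further difficulty: whether to run it, and how much weight to give it, could be decided after the per-site results are known.

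The endpoint deserves a clear answer because it measures sensation and not pain. Protocol 1.6.4 reports a favourable trend in monofilament testing in the Phase II trial, so readers will look for it here.

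**Working it through.** **Plan's own figure.** The documents state no error rate or power for this endpoint. Their sample size gives the group sizes used below. For the first primary endpoint (SAP 5: difference 1.0, SD 3.0, two-sided 0.05, ratio 2:1), sqrt(1/286 + 1/143) = 0.1024 and the noncentrality is 1.0 / (3.0 x 0.1024) = 3.25. The noncentral t-test then gives 90.1% power at 286/143, which reproduces the stated 90%.

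**Number of tests.** 5 sites x 2 feet (SAP 8.4.7) x 3 visits (SAP 4.3) = 30.

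**False positives with no drug effect, if each model is read at two-sided 0.05.**
- Expected number: 30 x 0.05 = 1.5, whatever the correlation.
- Chance of at least one if all tests were independent: 1 - 0.95^30 = 78.5%. In favour of VM202 only: 1 - 0.975^30 = 53%.
- The tests are not independent, and the documents give no correlations. The figures below are therefore assumptions shown as a range. They come from simulating 30 correlated normal test statistics (site correlation crossed with visit correlation, 2,000,000 draws per row).

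| Site correlation | Visit correlation | At least one p<0.05 | At least one favouring VM202 |
|---|---|---|---|
| 0.3 | 0.5 | 67.7% | 37.6% |
| 0.5 | 0.5 | 58.5% | 30.8% |
| 0.7 | 0.5 | 46.1% | 23.5% |
| 0.9 | 0.5 | 29.5% | 14.8% |
| 0.9 | 0.7 | 25.8% | 12.9% |

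**Power for an effect shared by all ten sites.** Assume 0.25 SD at every site, a value not in the documents, with 286/143 subjects and a normal approximation.
- One site: noncentrality 0.25 / 0.1024 = 2.44; power = Phi(2.44 - 1.96) = 0.68.
- Ten sites averaged, with correlation r between sites: multiply the noncentrality by sqrt(10 / (1 + 9r)).
  - r = 0.3: factor 1.64, power 0.98.
  - r = 0.5: factor 1.35, power 0.91.
  - r = 0.7: factor 1.17, power 0.82.
  - r = 0.9: factor 1.05, power 0.73.

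**After the fix.** One test at one named visit carries 5%. If all three visit-level tests were read without adjustment, the chance of at least one false positive would be 1 - 0.95^3 = 14.3% if independent, and by simulation 12.5% and 10.9% at visit correlation 0.5 and 0.7. This is why a main visit has to be named.

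**The case against.** The case for leaving the plan alone has several parts.

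- **The SAP does not exclude an overall model.** A reader might infer that no overall comparison is possible. That goes too far, because the SAP permits one. What stands is that it is not committed to and its role is not defined.
- **Reading each test at 0.05 is an inference.** SAP 7.4 sets the level per endpoint, and no section says that one positive site would count as success. This is right, and the error figures are conditional on that reading. SAP 8.1 does make two-sided 0.05 the default for inferential analyses, and nothing in the SAP prevents the reading.
- **Correlation between sites does not invalidate the models.** A reader might infer that correlated readings are mishandled. They are not: each model holds one reading per subject, so its standard error and p-value are sound. The issues are multiplicity and the missing summary.
- **A chance positive is not shown to be more likely than not.** Protocol 1.1.2 describes a distal, symmetric disease, and inclusion criterion 8 limits the symptom difference between legs, so high site correlation is plausible. At 0.7 to 0.9 the chance is below one half, and it is lower still when only results favouring VM202 are counted. This stands.
- **The power comparison uses an assumed effect** on a continuous scale for an ordinal grade, and the gain is small when sites are highly correlated. This also stands; the figures illustrate direction and rough size.
- **The Phase II link is loose.** The trend in Protocol 1.6.4 is described alongside the MNSI physical assessment and may not concern this ten-site graded test.
- **The endpoint is exploratory**, and modelling it site by site is a legitimate choice. That limits the consequence but does not supply the missing overall answer.

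**Conclusion.** The point holds, at low severity. The SAP turns one exploratory endpoint into 30 treatment comparisons without a committed overall result or a rule for applying 0.05 across them.

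Read at 0.05 each, at least one nominal positive by chance has a probability of about 26% to 68% over the assumed correlations. That is roughly 5 to 14 times the nominal 5% (25.8/5 = 5.2; 67.7/5 = 13.5). Between about 13% and 38% would see at least one favouring VM202. The power lost by testing a shared effect at one site is substantial at moderate site correlation and slight at 0.9.

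These sizes rest on correlations and an effect size that the documents do not give, and on the reading of SAP 7.4 described above. The count of 30, the 1.5 expected positives under that reading, and the absence of a committed joint analysis do not depend on the correlations.

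A reader might infer that the trial's error control is weakened. It is not: SAP 7.4 and 8.4.3 confine the hierarchical testing to the primary and secondary endpoints, and this endpoint lies outside it.

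**What to change.** Before unblinding, replace the optional wording in SAP 8.4.7 with a commitment to one joint cumulative-logit model containing all available sites for each subject. Keep the covariates already planned (stratification factor and baseline grade), and use a common treatment effect across sites with a robust within-subject variance. Estimate the treatment effect at each visit and name one visit as the main one.

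State that a site that cannot be tested is left out of that subject's contribution. The rule is needed because Protocol Appendix 6 tells testers to avoid callused, ulcerated or scarred skin, and the item-level rules in SAP 7.7.1 cover only the BPI-DPN and MNSI.

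Keep the per-site, per-visit shift tables and estimates as description, without significance claims.

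Keeping 30 tests with a Bonferroni level of 0.05/30 = 0.00167 would be a poor substitute. A site with 50% power at 0.05 would fall to Phi(1.96 - 3.14) = 12%.

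The cost is a few sentences in the SAP and one model to program, with no new data. The downside is that an effect confined to particular sites would be shown only descriptively.

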8.5. Safety Analyses

Safety analyses in this study will evaluate the safety profile of VM202, as compared with control. No formal statistical testing will be conducted for the safety analyses. The following sections summarize the descriptive analysis methods for these safety endpoints. All subjects in the Safety population will be included in these analyses. Subjects will be grouped by treatment administered. All summaries will be derived based on available data. No imputation will be performed for missing values.

8.5.1. Study Drug Exposure

Study drug exposure (number of injections and total volume administered per calf) will be summarized by treatment group for Day 0, Day 14, Day 90, Day 104, and overall using descriptive statistics for continuous variables.

8.5.2. Injection Site Reaction Assessments

The number and percentage of subjects with an injection site AE will be summarized descriptively overall and by type (injection site reaction, ulceration, allergic reaction/hypersensitivity) by treatment group and study visit. The number and percentage of subjects with a given type of injection site AE will be summarized by grade and treatment group for the pre- and post-injection assessments on Days 0, 14, 90, and 104; only subjects who receive an injection at a given one of these visits will be counted in the post-injection assessment results for that visit. Subjects without an injection site AE of a particular type will be assigned a grade of 0 for these summaries.

8.5.3. Adverse Events

All adverse event summaries will be restricted to Treatment Emergent Adverse Events (TEAE), which are defined as AEs that occur after dosing and pre-existing medical conditions that worsen following exposure to an investigational product. An AE with a missing start date and a stop date that is either missing or on or after the treatment start date will be considered as a TEAE. For summary purposes, verbatim terms reported by the study centers will be mapped to MedDRA (v21.0 or later) system organ classes (SOC) and preferred terms by the CRO and approved by the CDRC. It should be noted that only AEs that occurred after the first injection will be collected during the study.

The adverse event listings will be displayed by treatment group. The number of subjects experiencing a particular event, the percentage of subjects experiencing the event, and the total number of events will be presented. The following summaries will be created:

- TEAE by SOC and preferred term;
- TEAE by SOC, preferred term and protocol version;
- TEAE by SOC, preferred term and maximum severity. At the across-SOC and preferred term levels of subject summarization, a subject is classified according to the highest severity if the subject reported one or more events; severity within an SOC is not summarized. AEs with missing severity will be considered severe for this summary;
- TEAE by SOC, preferred term and closest relationship to study treatment (Related/Not Related). At each level of subject summarization, a subject is classified according to the closest relationship if the subject reported one or more

events. AEs with a missing relationship will be considered related for this summary; events classified as 'possibly', 'probably' or 'definitely' will be considered 'related'.

- Serious TEAEs by SOC and preferred term;
- TEAEs leading to study discontinuation by SOC and preferred term;
- Adverse events of special interest (AESI) by preferred term. Specific areas of special interest to be presented separately are for dizziness, somnolence, weight increase, peripheral edema, and falls as well as subsets of events within the Nervous System disorders, Investigations, and Injury, Poisoning and Procedural Complications system organ classes. The specific preferred terms within these subsets will be determined at the blinded data review.
- Injection Site Reactions (ISRs) included under AESI will include designations of relatedness and severity.

AESI summary tables will also be presented separately for each level of the randomization stratification factor.

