VM202 was evaluated for treatment of CLI in a prospective, double-blind, placebocontrolled, multicenter Phase II study. A total of 50 eligible 'no-option' CLI subjects with a Rutherford Scale score of 4 or 5 were randomized in 2:2:1 ratio to a low dose of VM202, high dose of VM202 or placebo. Subjects received a final dose of mg VM202, mg VM202 or placebo by IM injections in the affected, unilateral calf on \overline{D} ays 0, 14, 28, and 42. All subjects were followed for one year from the time of the first dose of study drug administration. Clinical evaluations were conducted at Day 0 (baseline), 14, 28, 42, 49, 90, 180, 270, and 365.

Efficacy was evaluated in the Efficacy Population (n = 50, defined as subjects that received all study injections). Improvements were statistically significant for wound healing in both treatment groups.

- Ulcers improved most in the high dose group when compared to placebo. The average decrease in wound area in the high dose group was 2.8 cm² (SD 0.3 cm²). Nine of the 14 ulcers present at baseline in the high dose group completely healed (9/14, 64.3%); all but one ulcer that did not completely heal showed improvement.
- Fourteen of 27 (14/27, 51.9%) ulcers in the low dose group healed; of the 13 that did not completely heal, 8 (8/13, 61.5%) improved (average decrease 1.3 cm², SD 1.1 cm^2).
- Only one ulcer present at baseline in the placebo group healed (1/9, 11.1%). The average *increase* in wound area in the placebo group was 4.3 cm² (SD 12.6 cm²).

Improvements in skin perfusion (as measured by TcPO₂) in both treatment groups were also significantly improved in the dorsum foot when compared to placebo in both treatment arms (low dose, p = 0.0299; high dose, p = 0.0681; treatment groups combined, p = 0.0475).

By the 3-month study visit, all three study arms experienced a reduction in pain with sustained reductions over the 12 month follow-up period, but only the two treatment arms had a statistically significant reduction compared to baseline. There was a greater relative reduction in pain from baseline in the high dose group at 6 and 9 months (-21.8, p=0.008, and -33.4, p=0.0018, respectively).

ABI and TBI trended towards improvement over the course of the study in all three study arms, but there were no statistically significant differences between treatment groups.

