There was no statistically significant difference in Rutherford scores across treatment groups at any time, but a pairwise comparison to baseline in the low dose group demonstrated a statistically significant improvement at 6, 9 and 12 months (p = 0.0016, p = 0.0012, p = 0008, respectively).

When considering the biological activity of VM202, amputation rates were lower in the low dose and high dose groups (2.5%) as compared to the placebo group (20%).

Intramuscular injections of VM202 in the lower leg were well tolerated. There were no unexpected adverse events in the study. Overall, 26 subjects experienced 67 serious adverse events over the course of the study (26/52, 50%). With the exception of thrombosis in the high dose group (placebo = 0%, low dose = 0%, high dose = 15%), there was no significant difference in the incidence of SAEs across treatment groups. One incident of peroneal deep vein thrombosis was categorized as possibly related to the study injection. All other SAEs were deemed unrelated to the study drug / placebo. The majority of SAEs were related to the natural progression of peripheral arterial disease (PAD).

In conclusion, VM202 significantly improved wound healing, improved skin perfusion (as measured by TcPO2), and reduced pain. Positive trends were seen in Rutherford classification and in measureable pressures (ABI/TBI). There appeared to be a significant dose response. The number and types of adverse events seen in this study were consistent with those reported in the literature for other interventional studies in patients with CLI. VM202 continues to demonstrate an excellent safety profile.

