All screening assessments should occur within the 90 days prior to Day 0 (day of first injections), and the diary must be completed within 14 days prior to Day 0.

Randomization. Subjects who meet the eligibility criteria will be randomly assigned in a 2:1 fashion to one of the two treatment arms: VM202 (32 mg VM202 total dose, 16 mg / leg), or placebo, respectively. Randomization will be stratified by current use of gabapentin and/or pregabalin. Assignment to a treatment arm will be centralized, using an independent predetermined randomization scheme in a double-blinded fashion. Blinding will be achieved by having the study medication (VM202 and placebo [VM202 vehicle]) prepared by the study pharmacist. Reconstituted VM202 is indistinguishable from the VM202 vehicle.

First Treatment. Prior to the first injection, vital signs, concomitant medications, VAS, BPI-DPN, Semmes-Weinstein monofilament testing, and nerve conduction (only at select sites), testing will be conducted. In addition, blood will be drawn for determination of serum chemistry and hematology, HbA1c, serum HGF, and copies of VM202.

Subjects will receive VM202 or placebo (VM202 vehicle) by intramuscular injections in both legs (in the calf) on Day 0, and Day 14 as follows:

Table 2. First Treatment: Day 0 and 14

TREATMENT GROUP	DOSE VM202 (mg)/Visit/Leg	FINAL DOSE	FINAL DOSE VM202 / SUBJECT / TREATMENT (mg)	
	DAY 0	DAY 14	VM202 / LEG (mg)		
VM202 Placebo	4 0	4 0	8 0	16 0	

0 = injections of VM202 vehicle

All subjects will receive sixteen (16) 0.5 mL injections evenly distributed over each calf at each visit of VM202 or placebo.

Subjects randomized to the VM202 treatment arm will receive the following intramuscular injections in each calf:

- Day 0 16 injections of 0.5mL of VM202 / calf
- Day 14 16 injections of 0.5mL of VM202 / calf

Subjects randomized to the placebo control group will receive the following intramuscular injections in each calf:

- Day 0 16 injections of 0.5mL of VM202 vehicle / calf
- Day 14 16 injections of 0.5mL of VM202 vehicle / calf

Note: Visually, VM202 vehicle is indistinguishable from reconstituted VM202. The subject and clinician will not be able to distinguish placebo from VM202 injections.

1 to 3 hours post injection on Day 0 and Day 14, vital signs, and blood draw for determination of copies of VM202 will be performed, and the occurrence of injection site reactions and adverse events will be assessed.

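### SAP 8.5.3 plans no grouped row for thrombotic events, the only SAE category the protocol reports as raised on VM202

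*SAP*

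**What the plan says.** **AESI list.** SAP 8.5.3 states: "Specific areas of special interest to be presented separately are for dizziness, somnolence, weight increase, peripheral edema, and falls". Two further sources follow. One is subsets of three system organ classes (nervous system; investigations; injury and procedural complications), with the terms to be settled at the blinded data review. The other is injection site reactions, shown with relatedness and severity. AESI are tabulated by preferred term. Neither thrombosis nor any vascular or thromboembolic group is named.

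**Earlier signal.** Protocol section 1.6, under the phase II study in critical limb ischemia, reports: "With the exception of thrombosis in the high dose group (placebo = 0%, low dose = 0%, high dose = 15" (percent), and says that otherwise "there was no significant difference in the incidence of SAEs across treatment groups". It continues: "One incident of peroneal deep vein thrombosis was categorized as possibly related to the study injection". All other SAEs in that study were judged unrelated.

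**How safety will be read.** SAP 8.5 plans description only, with no formal testing. Thrombotic events would appear in the tables of all and of serious treatment-emergent events, by system organ class and preferred term. Under protocol 6.3.6 and SAP 7.5, the DSMB sees a limited set of unblinded tables or listings that includes all reported AEs.

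**The concern.** Without formal safety testing, detection depends on what each table row shows. Thrombosis can be coded under more than one preferred term. The system organ class rows do add terms together, but they mix thrombotic events with everything else in the class. No planned row counts subjects with at least one thrombotic event. The product is again injected into the calf in this trial, and safety is one of its stated objectives, so a reader would expect a pre-specified look at the one SAE category singled out in the product's own history. A grouping first built after unblinding would be open to the charge that its terms were chosen to suit the result.

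The injection-site form could divide the events further. Protocol 4.2.14 uses calf location and timing after injection to decide whether an event is an injection site reaction or an adverse event. Its Table 5 mentions phlebitis as part of a Grade 2 reaction. SAP 8.5.2 then summarises that form under three types: reaction, ulceration and allergy. A calf thrombosis soon after injection might therefore be recorded apart from the others.

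**Working it through.** **1. The earlier figure.** The protocol gives "A total of 50 eligible 'no-option' CLI subjects", who "were randomized in 2:2:1 ratio to a low dose of VM202, high dose of VM202 or placebo". That implies 50 × 2/5 = 20 high-dose, 20 low-dose and 10 placebo subjects. The number of thrombosis cases is not stated. 3/20 = 15.0% matches, while 2/20 = 10% and 4/20 = 20% do not. The SAE sentence uses 52 as its denominator; with 21 high-dose subjects, 3/21 = 14.3%. So 3/20 is the likely count, but it is inferred.

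**2. Strength of that signal, on 3/20.** The exact 95% interval is 3.2% to 37.9%. Two-sided Fisher tests give:
- against placebo (0/10): p = 0.53
- against low dose (0/20): p = 0.23
- against both combined (0/30): C(20,3)/C(50,3) = 1140/19600, so p = 0.058

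**3. The same product in DPN.** In the phase II DPN study (protocol 1.6.4), subjects with an SAE were 4/43 (9.3%) on high dose, 3/39 (7.7%) on low dose and 3/21 (14.3%) on placebo. All SAEs were classed as unrelated.

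**4. Pooled against split rows.** The planned VM202 arm is 318 (SAP section 5). The true rates, the number of terms and the even split are my assumptions. With rate r over k terms, the count in one row is Binomial(318, r/k), with mean 318r/k.

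| Assumed rate | Pooled: mean, P(≥5) | One of 3 rows: mean, P(≥5) | One of 5 rows: mean, P(≥5) |
|---|---|---|---|
| 1% | 3.2, 22% | 1.1, 0.5% | 0.6, 0.1% |
| 2% | 6.4, 76% | 2.1, 6% | 1.3, 1% |
| 3% | 9.5, 96% | 3.2, 22% | 1.9, 4% |
| 15% | 47.7, about 100% | 15.9, about 100% | 9.5, 96% |

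A reader scans every row, so the chance that at least one of three rows reaches 5 is the fairer comparator. At 2%, treating rows as independent, it is 1 − (1 − 0.063)³ = 18%, still far below 76%. The threshold of 5 is only a marker for a count that catches the eye.

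**5. What pooling cannot do.** Set against 0/159 on placebo, pooled counts of 3, 6 and 10 among 318 (about 1%, 2% and 3%) give two-sided Fisher p = 0.55, 0.19 and 0.035. Pooling makes an excess visible; at 1% to 2% it would not make it conclusive.

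**The case against.** The strongest reply is that nothing is lost. Every thrombotic event is collected, tabulated by system organ class and preferred term, repeated in the serious, severity and relatedness tables, and available to the DSMB. The existing AESI are shown by preferred term, so a pooled row is a new kind of table and not equal treatment with the five named events. If all cases were coded to one term, they would stay together anyway. All of this stands, and it limits the point to presentation.

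Four stronger readings are tempting, and the documents do not support them:
- *The plan would hide a repeat of the CLI signal.* It would not. 15% of 318 is about 48 subjects, and even a five-way split leaves 9.5 per row.
- *VM202 carries an established dose-related thrombosis risk that applies here.* The data are about three subjects with no-option limb ischemia, injected in one calf on Days 0, 14, 28 and 42. The low-dose arm had none, only one event was thought possibly related, and the DPN study showed no difference. The CLI doses are redacted, so exposure cannot be compared with this trial.
- *The blinded review is barred from adding vascular terms.* The SAP places the open choice of terms inside three classes but does not call the AESI list closed. Which thrombotic terms fall in those classes depends on dictionary coding that the documents do not show. What can be said is that the SAP commits to none.
- *The three class subsets are the only other AESI source.* Injection site reactions are a further one and might catch some calf events, though nothing ensures it.

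**Conclusion.** The point holds as a cheap improvement to the safety tables, not as a fault that endangers the trial's conclusions. The SAP names several AESI but no thrombotic group, while thrombosis is the only SAE category the protocol reports as raised on VM202. The practical gap is a modest excess, for example 1% to 3%, spread over several preferred terms with no planned row to add it up. At 2%, the chance of seeing at least 5 VM202 subjects falls from 76% in a pooled row to 6% in any given one of three equal rows, or about 18% in at least one of them. These figures rest on assumed rates and an assumed even split, and they shrink to nothing if coding uses a single term. The inferred 3/20 does not establish a risk. It is a reason to specify the look in advance.

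**What to change.** In SAP 8.5.3, add an AESI group for venous and arterial thrombotic and embolic events.
- **Terms:** settle the preferred-term list at the blinded data review, drawing on all system organ classes and on events recorded on the injection-site form.
- **Summary:** number and percentage of subjects with at least one event, by actual treatment in the safety population. Add a descriptive risk difference with a 95% interval that copes with zero counts, such as Miettinen–Nurminen.
- **Detail:** seriousness, relatedness and days since the last injection. Protocol 5.2 already collects onset date, seriousness and relatedness. Leg is not among the AE fields listed there, so show it only where it has been recorded.

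The cost is a paragraph of SAP text and one more table, with no new data collection and no change to study conduct. The downside is that some background events unrelated to the drug will be counted in the group; the placebo column shows how many to expect.
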